3.2 Secondary Objectives

The following secondary objectives will be used to support the results of the primary objective:

1. Assess independent effects of three active concentrations of marijuana and placebo in reducing self-reported symptoms of PTSD with the PCL-5, anxiety and depression with the IDAS, and improving psychosocial functioning with the IPF and WBR (self-report and observer) among veterans during Stage 1.
2. Assess independent effects of three active concentrations of marijuana and placebo in reducing self-reported symptoms of PTSD with PCL-5, anxiety and depression with IDAS, and improving psychosocial functioning with the IPF and WBR (self-report and observer) among veterans during Stage 2.
3. Assess comparative efficacy between placebo and each active dose of marijuana based on a within-subjects analysis of PTSD symptoms as measured by the CAPS-5 in crossover participants at Baseline, End of Stage 1, Stage 2 Baseline, and End of Stage 2.
4. Assess whether Stage 2 crossover participants' preferences for marijuana concentrations in Stage 1 and Stage 2 correlate with reduction in PTSD symptoms as measured by the CAPS-5 total score.
5. Assess whether participants experience a clinically significant increase in PTSD symptoms based on CAPS-5 and PCL-5 total scores during the washout period between Stage 1 and Stage 2 compared with measures assessed at Baseline and during Stage 1.
6. Explore correlation of treatment outcomes measured by CAPS-5 score with objective changes in sleep via Actigraphy throughout the study and self-reported

- changes in sleep quality using the ISI on a weekly basis.
7. Explore correlation of Daily Diary items related to sleep with objective changes in sleep via Actigraphy and self-reported changes in sleep quality using the ISI on a weekly basis.
 8. Explore correlation of treatment effects measured by CAPS-5 total score with amount of marijuana used based on Daily Diary across Stage 1 and Stage 2.
 9. Explore treatment outcomes measured by CAPS-5 total score by marijuana concentration, with concomitant substance and medication use as a covariate throughout the treatment period.
 10. Explore durability of treatment outcomes measured by CAPS-5 total score, with any PTSD treatments based on the LTFU questionnaire treated as a covariate, six months after completing Stage 2.

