4.3.1 Participant Inclusion Criteria

Eligible individuals based on initial screening criteria must:

1. Meet DSM-5 criteria for chronic PTSD of at least six months duration.
2. Have PTSD of at least moderate severity (CAPS-5 score of 25 or more) at the time of baseline assessment.
3. Be a military veteran with primary index trauma of combat service-related PTSD.
4. Have treatment-resistant PTSD, defined as meeting DSM-5 diagnostic criteria for PTSD after failing on, or being unable to tolerate, FDA-approved medication or empirically supported psychotherapy for PTSD of adequate dose and duration, as determined on a case-by-case basis by the site CI.
5. Be at least 18 years old.
6. Be willing to commit to medication dosing and delivery method, to completing evaluation instruments, and attending all study visits.
7. Agree to use only marijuana provided by site staff and agree to required cessation periods for the duration of the study.
8. Report no current hazardous marijuana use, as defined by a score of < 8 on the CUDIT-R at time of screening, and completely abstain from marijuana during the 2-week baseline assessment period (biochemically verified via urine and/or blood cannabinoid concentrations).
9. Agree to video record all marijuana administrations and provide video to the site staff for review during study participation.
10. Agree to keep all marijuana provided by site staff securely stored in the provided lock box and not to share/distribute marijuana to any other individual.
11. Provide a qualified self-appointed community observer who they interact with an average of at least twice per week in the prior month and can knowledgeably report on at least 2 domains of the Weekly Behavior Report as judged by study staff.
12. Be stable on any pre-study medications and/or psychotherapy regimen for PTSD prior to study entry, agree to inform physician(s)/clinician(s) providing current care about participation in the study, and agree to report any changes in medication or psychotherapy treatment regimen during the study, to study staff.

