5.1.2 Safety Measures

The Time-Line Follow-Back (TLFB) method will be used to track medical and non-medical drug/substance use [88, 89]. A retroactive TLFB assessment will be conducted to record substance use during the 90-days prior to the intake assessment during screening. It will then be repeated at the six-month follow-up visit to collect substance and medication use for each day since the last visit.

The Cannabis Use Disorders Identification Test-Revised (CUDIT-R) [90] is an eight-item self-report questionnaire used to assess problematic marijuana use within the past six-months. Questions assess consumption (frequency), marijuana abuse (e.g., use in hazardous situations, inability to fulfill obligations), marijuana dependence (e.g., not able to stop using, spending a lot of time obtaining, using, or recovering from use), and negative consequences of use (e.g., problems with memory or concentration). Responses are summed, thus providing a continuous score of problematic marijuana use. The CUDIT has demonstrated high internal consistency and acceptable test-retest reliability, high specificity and sensitivity, as well as satisfactory predictive power [90].

The Marijuana Withdrawal Checklist (MWC) [91, 92] will be used to assess the presence of marijuana withdrawal symptoms during prior periods of abstinence. The MWC will be labeled the Behavior Checklist to minimize expectancy effects. It lists 32 symptoms for which participants indicate severity on a four-point scale (0=not at all, 1=mild, 2=moderate, 3=severe). The symptom list comprises the valid items found in prior marijuana withdrawal studies and additional non-specific items to minimize response bias. During the intake assessment, participants will be instructed to indicate whether and to what degree they experienced each symptom during past periods of marijuana abstinence lasting at least 48 hours, if they are current marijuana users. Instructions will be slightly different during the study than during the intake assessment. Participants will be asked to rate how they have felt since last completing the questionnaires. Administered in this way, the MWC has been used effectively to detect reliable marijuana withdrawal effects in several prior studies [91-96]. A total withdrawal discomfort score (WDS) will be computed from the Checklist and will be the outcome variable for this measure. This summary score will include the symptoms reliably observed in prior marijuana withdrawal studies [97].

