5.1.3 Process Measures

The Daily Diary is an instrument developed by the sponsor to track AEs and assess daily use of study marijuana as well as other substances. The Daily Diary will be an electronic data capture form completed on an electronic device. Information collected with this diary will include participants' self reported quality and duration of sleep, the daily amount of marijuana used concomitant use of alcohol, medications, or other drugs, as well as AEs. Daily diary reports will be confirmed and verified by phone contact, reviewing video of participants' self-administration of marijuana, and qualitative urine drug testing at the sites.

The LTFU questionnaire is a sponsor-developed self-report instrument that will gather information on current psychiatric health and wellbeing, including the occurrence of new traumatic events, and questions concerning the number and type of new treatments for PTSD the participant has undergone since his or her final visit during the treatment period. The LTFU questionnaire takes approximately five minutes to complete, and will be completed by the participants at the six-month follow-up.

Laboratory testing of blood/urine cannabinoids will be conducted by an accredited laboratory with an appropriately sensitive, specific and validated assay, as specified in Section 10.2. Peripheral blood samples will be collected and stored for biomarker analysis of cannabinoids (THC, 11-OH-THC, THC-COOH), CBD metabolites and inflammation markers with appropriately sensitive, specific and validated assays for CRP, IL-1 β , and IL-6. Peripheral blood will be drawn at specified times in the Time and Events Labs table and analyzed according to procedures described in Section 10.0.

Questions regarding the belief of condition assignment and certainty of the belief will be asked of site staff and participants at the End of Stage 1 and End of Stage 2. These beliefs are collected as a part of the sponsor's ongoing initiative to optimize the double-blind as a part of drug development studies.

Table 1: Time and Events (Administrative Procedures)

| | Screen | Baseline | | Stage 1 | | | Cessation 1 | | Stage 2 | | | Cessation 2 | | Stage 3 | LTFU |
|---------------------------------|---|----------------------------|--|---|---|--|-----------------------------------|---|--|---|---|-------------------------------------|---|-------------------------------------|--|

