5.2.4 Enrollment

Day 0 of the study will be the day of enrollment. Enrollment will be completed after the two-week screening period and obtaining quantitative Cannabinoid Results from applicable participants.

- a) Inquire about any possible changes in the participant's health to ensure they continue to meet eligibility criteria.
- b) After eligibility is confirmed, the candidate may be enrolled. Issue a participant number.
- c) The CI or site staff will schedule introductory sessions and the beginning of the period of active dosing.
- d) Collect information on any changes in psychotherapy or medications for the participant.
- e) Participants will receive a research participant identification card ("wallet card") stating that they are a research participant and may test positive for drugs and

- listing CI contact information, the telephone number for a 24-hour hotline for participant support, and instructions on how and when to present the card.
- f) Obtain/confirm the name and telephone number of an emergency contact from the participant for use throughout the study.
 - g) The participant will complete the IDAS, ISI, IPF, WBR, PCL-5, MWC, and Daily Diary.
 - h) Site staff will contact the community observer for completion of the WBR.
 - i) The CI or qualified site staff will administer the CSSRS and GWB.
 - j) Perform a urine-dip EtG test on all participants to assess alcohol consumption.
 - k) Randomization will occur after enrollment and prior to the day of the first introductory session.
 - l) Throughout the study, concomitant medications and therapies and AEs will be collected at each contact as described in Sections 8.0 and 9.0 of the protocol.

5.2.5 Introductory Sessions in Stage 1 (Visit 1 and Visit 2) and Stage 2 (Visit 8 and Visit 9)

This visit will be conducted one week after the Screen 2 visit. To standardize method of self-administration and to assess psychological risk, this protocol will include two four-hour long introductory sessions, where the participants will self-administer marijuana under observation and receive training, on two consecutive days as an added safety procedure prior to the initiation of each treatment phase.

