9.0 Collection of Concomitant Medications and Therapies

Information about all concomitant prescription medications, and only over the counter (OTC) medications associated with an AE, will be collected from screening up to the day of the final study visit in Cessation 2 or Stage 3, as applicable, including reasons for use, date started, date ended and dose information if available. During the follow-up period after this visit and before the six-month follow-up, information on new psychiatric medications will be gathered on the day of the six-month follow up study visit. During the follow-up period, healthcare utilization associated with AEs requiring medical attention and psychiatric AEs will be collected. Medications recorded per protocol, including medications taken to treat AEs, will be recorded on a concomitant medications form eCRF. Information on participation in evidence-based psychotherapy for PTSD will be collected throughout the study. Therapies and healthcare utilization recorded per protocol will be recorded on a concomitant therapies form eCRF.

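### Secondary Objective 9 adjusts the CAPS-5 comparison between concentrations for substance and medication use measured after randomization, so it does not estimate the randomized effect and may be biased in either direction

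*Protocol*

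**What the plan says.** Objective 9 in protocol Section 3.2 is to "Explore treatment outcomes measured by CAPS-5 total score by marijuana concentration", "with concomitant substance and medication use as a covariate throughout the treatment period". The section opens by giving its whole list a role: the "secondary objectives will be used to support the results of the primary objective".

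The timing of the covariate follows from other sections:

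- Section 5.2.4: "Randomization will occur after enrollment and prior to the day of the first introductory session". Anything recorded during Stage 1 or Stage 2 therefore comes after Stage 1 assignment.
- Section 5.1.3: the Daily Diary captures "concomitant use of alcohol, medications, or other drugs, as well as AEs".
- Section 9.0: prescription medication data "will be collected from screening up to the day of the final study visit in Cessation 2 or Stage 3".
- Section 4.3.1, item 12: regimens must be stable before entry, but participants only "agree to report any changes in medication or psychotherapy treatment regimen during the study, to study staff". Change on study is foreseen.

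A pre-randomization measure also exists. Section 5.1.2 states: "A retroactive TLFB assessment will be conducted to record substance use during the 90-days prior to the intake assessment during screening". Objective 9 does not restrict its covariate to that measure.

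The primary analysis in Section 12.0 is an ANCOVA of CAPS-5 at baseline and end of Stage 1, with concentration and time as factors. Concomitant use is not listed in it.

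**The concern.** A covariate measured before randomization can sharpen a treatment comparison without distorting it. A covariate that treatment can change does not have that property. Conditioning on it takes out whatever part of the effect runs through it. If it shares an unmeasured cause with the outcome, such as underlying severity, conditioning also makes the arms differ on that cause.

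The protocol gives reasons to expect such a covariate here:

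- Section 2.2.1 says patients with PTSD may use alcohol, benzodiazepines and marijuana to self-medicate hyperarousal. A treatment that changes symptoms could change that use.
- Section 2.2.2 says benzodiazepines and related drugs are used for anxiety and sleep disruption in PTSD. Medication could therefore change symptoms.
- Alcohol and drug use is one domain of the Weekly Behavior Report (Section 5.1.1), which Secondary Objectives 1 and 2 treat as an outcome of the assigned marijuana. Objective 9 then uses the same kind of behaviour as an adjustment variable.

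What is at stake is interpretation. A secondary contrast that randomization does not protect may be cited for or against the primary finding.

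**Working it through.** The protocol attaches no figure to Objective 9, so there is none to reproduce. The check is algebraic, with assumed inputs.

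**Model for one active-versus-placebo contrast, in SD units**

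- *T*: total treatment effect on CAPS-5 (negative means improvement). Set to -0.40 as a scale only. Section 12.1 assumes an effect size of 0.4, but nothing below depends on how that figure is read.
- *a*: effect of treatment on concomitant use, with the covariate's within-arm SD equal to 1. Assumed.
- *b*: effect of concomitant use on CAPS-5. Assumed.
- *u_M*, *u_Y*: loadings of an unmeasured common cause on use and on CAPS-5. Assumed.

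**Formula**

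The direct effect is T - ab. Given arm and covariate, the expected value of the common cause contains the term -a·u_M, which adds -a·u_M·u_Y to the treatment coefficient. Hence:

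- unadjusted coefficient = T
- coefficient adjusted for on-treatment use = T - a(b + u_M·u_Y)
- bias for the total effect = -a(b + u_M·u_Y)

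**Results**

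| a | b | u_M, u_Y | Bias | Adjusted, T = -0.40 | Adjusted, T = 0 |
|---|---|---|---|---|---|
| 0 | any | any | 0 | -0.40 | 0 |
| -0.25 | 0.3 | 0, 0 | 0.25 × 0.30 = 0.075 | -0.325 | +0.075 |
| -0.25 | 0 | 0.5, 0.5 | 0.25 × 0.25 = 0.0625 | -0.3375 | +0.0625 |
| -0.25 | 0.3 | 0.5, 0.5 | 0.25 × 0.55 = 0.1375 | -0.2625 | +0.1375 |
| -0.5 | 0.3 | 0, 0 | 0.5 × 0.30 = 0.15 | -0.25 | +0.15 |
| -0.5 | 0 | 0.5, 0.5 | 0.5 × 0.25 = 0.125 | -0.275 | +0.125 |
| -0.5 | 0.3 | 0.5, 0.5 | 0.5 × 0.55 = 0.275 | -0.125 | +0.275 |
| -0.5 | -0.3 | 0, 0 | 0.5 × (-0.30) = -0.15 | -0.55 | -0.15 |

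A simulation of the same model (500,000 subjects per scenario) agreed with every row except the last to within about 0.005. For example, it gave -0.325, -0.339 and -0.266 for a = -0.25. The unadjusted estimate stayed between -0.396 and -0.404 when T = -0.40. The last row rests on the algebra alone.

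**Reading the table**

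- There is no bias if treatment leaves use unchanged (a = 0), or if use neither affects CAPS-5 nor shares a cause with it.
- If marijuana lowers use and use raises CAPS-5, a true benefit is attenuated and a true null looks like harm.
- If marijuana lowers the use of medication that itself lowers CAPS-5, the benefit is exaggerated.
- If marijuana raises use (a > 0), each shift changes sign.

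Objective 9 pools substances and medication in one covariate. Components with opposite signs of *b* may be mixed, so even the direction cannot be predicted.

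**The case against.** Much can be said for the plan.

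- **The primary analysis is clean.** The Section 12.0 model does not list the covariate, ITT data are used, and Objective 9 feeds no decision rule. Section 12.1 calls the study a pilot. This stands. A reader might infer that the adjustment could corrupt the primary result; the documents do not support that.
- **The item is exploratory.** Items 1 to 5 of Section 3.2 are worded as assessments and items 6 to 10 as explorations. This lowers the stakes. It is not a full answer, because the lead sentence gives all ten a supporting role, and Section 3.4 has a separate list of exploratory analyses meant to inform future studies, where this item was not placed.
- **The question is legitimate.** Participants may stay on medications and therapies (Section 7.2), so asking whether differences persist given other use is reasonable. That is true, but it is a mediation-type or descriptive question and the objective does not say so. A SAP could specify the model, but the protocol already names the covariate and its timing.
- **The bias may be nil or small.** Regimens must be stable at entry, current substance use disorders other than marijuana, caffeine or nicotine are excluded (Section 4.3.2), and stages last three weeks. Nothing in the documents supports any particular shift in use. This stands. A reader might infer a known percentage loss, or that the adjustment must hide part of a benefit; neither size nor direction can be derived.
- **Reporting by arm is already planned.** Section 12.0 foresees summary tables of the Daily Diaries and concomitant medications by concentration group. This stands, and nothing new is needed there.

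**Conclusion.** The point holds in a limited form. Followed as written, Objective 9 yields a contrast between concentrations that is conditional on a post-randomization variable which the protocol's own rationale says may respond to treatment. That contrast does not estimate the randomized total effect and may be biased towards or away from zero. The shift is -a(b + u_M·u_Y), and the documents supply none of its terms. The values from -0.12 to -0.55 around a true -0.40 are illustrations under assumed inputs, and the shift is zero if treatment does not change use. The primary analysis is unaffected. The consequence is a secondary estimate that could be misread as evidence for or against the primary result.

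**What to change.** Reword Objective 9 so that the covariates for the concentration comparison are substance use before randomization (the 90-day Time-Line Follow-Back at screening) and medication at baseline (collected from screening under Section 9.0). Keep on-treatment substance and medication use in the by-group summaries already planned in Section 12.0. If an analysis adjusted for on-treatment use is retained, label it descriptive or mediation-type and state that it is not used to support the primary result.

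The cost is a change of wording in Section 3.2, carried into the SAP. The baseline data are already being collected. There is one small loss: the baseline-adjusted analysis no longer addresses whether differences between concentrations persist given use during treatment. The separately labelled analysis can address that if it is wanted.

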3.3 Safety Objectives

The safety of participants will be measured throughout the study by assessing physiological and subjective drug effects, psychological distress, adverse events (AEs), and suicidality, repeatedly as described in the following steps. Summaries of safety data by study stage will be provided to the Medical Monitors for review during the study.

1. Explore correlations of subjective effects with the DEQ and cardiovascular effects with heart rate of each active dose of marijuana and placebo during introductory sessions.
2. Explore independent effects of each active dose of marijuana and placebo on blood pressure and body temperature during introductory sessions.
3. Assess independent effects of each active dose of marijuana and placebo on marijuana withdrawal symptoms during screening and Cessation 1 and 2.
4. Assess independent effects of each active dose of marijuana and placebo on problems associated with marijuana use during the study, including follow-up, with the CUDIT-R.
5. Evaluate the subjective effects of each active dose of marijuana and placebo in both controlled laboratory and outpatient settings, including ratings of unpleasant drug effects, using the DEQ and Daily Diary entries.
6. Assess independent effects of each active dose of marijuana and placebo on suicidality with the CSSRS on a weekly basis throughout the treatment period, and more frequently if needed.
7. Assess independent effects of each active dose of marijuana and placebo on whether and for how many days participants were incarcerated throughout the study.
8. Assess independent effects of each active dose of marijuana and placebo on whether and for how many days participants were hospitalized throughout the study.
9. Assess metabolites of alcohol use through urine testing at face-to-face visits.
10. Collect, review, and report Serious Adverse Events (SAEs) and AEs in accordance with FDA regulations and Section 8.0 of the protocol.

3.4 Process Objectives

The following objectives will include exploratory analyses intended to inform future studies:

1. Evaluate protocol compliance based on comparison of Daily Diary entries, including information on amount, time and frequency of marijuana use, and the weight of any unused marijuana across each study stage.
2. Evaluate protocol compliance using quantitative blood and/or urine cannabinoid levels.
3. Evaluate whether markers of inflammation CRP, IL-1 β , and IL-6 levels in blood predict PTSD severity at baseline and treatment outcome as a function of marijuana concentration.
4. Assess the ability of site staff and participants to accurately guess condition assignment in Stage 1 and Stage 2.

